Vital signs		Refer to Table 17											
ECOG performance status ¹³	X	X				X			X			X	
Hematology ¹⁴	X	X		X	X	X	X	X	X	X	X	X	
Serum chemistry ^{15,16}	X	X		X	X	X	X	X	X	X	X	X	
Coagulation ¹⁷	X	As clinically indicated											X
Urinalysis ¹⁸	X											X	
Pregnancy test ¹⁹	X	X				X			X			X	X
Archival/baseline tumor biopsy	X												
Tumor markers ²⁰		As clinically indicated											
Biopsy (fixed and frozen) and plasma biomarker sample ²¹	X (Parts A, B only)		X (3 to 5 days post C1D1)										
Plasma PK and ADA		Refer to Table 18 (Parts A and A2) and Table 19 (Part B)											

See footnotes on the following page.

Table 13. Schedule of Procedures: Parts A, A2, and B

Note: For Parts A, A2, and B, each cycle constitutes 21 days.

1. Study visits that cannot occur on the scheduled day due to unforeseen circumstances other than toxicity (eg, weather or holidays) should be completed as close to the scheduled date as possible. Laboratory assessments may be performed up to 2 days prior to the visit or as otherwise specified in the Schedule of Procedures. Visits conducted outside the windows are to be discussed with the Medical Monitor or designee in advance.
2. Medical history to include confirmation of previous cancer diagnosis, and record cancer treatment history, current symptoms at baseline, and current medications, as well as those taken within 30 days of first dose of study drug. An ophthalmology history is also required.
3. AEs will be assessed and reviewed prior to infusion and at any other visit that includes a physical examination.
4. Concomitant medications will be assessed and reviewed prior to infusion and at any other visit that includes a physical examination. Changes in concomitant medications will be collected up to and including the EOT Visit. After EOT, only concomitant medications administered for irAEs occurring within 90 days after last dose will be recorded. Once a subject enters the Follow-Up Period, only new therapies for the treatment of their cancer should be recorded in the eCRFs.
5. CX-2009 will be administered by IV infusion every 21 days. There must be a **MINIMUM** of 21 days between infusions (a window of ± 2 days may occur). CX-2009 will be administered over 90 (± 10) minutes with careful monitoring of IRRs.

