12. The ocular symptom assessment will include assessment of blurred vision and ocular discomfort. The ocular symptom assessment will be performed at Screening, Day 1 of every cycle, and at the EOT Visit. If ocular toxicity occurs, see Section 5.5.3.2 and Section 5.5.4.1.
13. ECOG performance status should be assessed at Screening, Day 1 of every cycle, prior to each infusion, and at the EOT Visit.
14. Including CBC with differential, including platelet count and reticulocyte count, will be performed at Screening, preinfusion, weekly during treatment, and at the EOT Visit.
15. Serum chemistry will include ALP, AST/SGOT and ALT/SGPT, total bilirubin, calcium, phosphorus, BUN, creatinine, total protein, albumin, glucose, potassium, sodium, chloride, magnesium, uric acid, LDH, and hemoglobin A1c, if clinically indicated. Blood glucose should be fasting at Screening and as indicated to evaluate possible hyperglycemia. Calculated creatinine clearance is required at Screening. Laboratory assessments drawn on the day of infusion should be drawn preinfusion.
16. Serum chemistry will only include electrolytes (potassium, sodium chloride, and magnesium) on Day 8 and Day 15 of every cycle.

Table 13. Schedule of Procedures: Parts A, A2, and B

Page 4 of 4

17. Coagulation will include PT/aPTT/INR at Screening, the EOT Visit, and as clinically indicated. If results are abnormal at Screening, then repeat prior to dosing or as clinically indicated.
18. Urinalysis (including assessment of protein, blood, leukocytes, glucose, ketones, bilirubin, urobilinogen, pH, and specific gravity) with microscopic examination at Screening and the EOT Visit.
19. Serum pregnancy test (HCG) should be evaluated in all women of childbearing potential at Screening. If the Screening serum pregnancy test is obtained within 7 days of first infusion, the Day 1 pregnancy test may be omitted. Urine pregnancy test (with serum test as needed for confirmation) should be obtained prior to each cycle of therapy, at the EOT Visit, and at FU/EOS Visits through 50 days after the last dose of CX-2009.
20. Tumor marker assessments should be scheduled concurrently with CT for PSA and CA125 for appropriate tumor types; all others as clinically indicated.

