10. A targeted physical examination should be performed weekly during the DLT period, prior to each infusion, and as needed by subject symptoms or clinical observations, focused on key organ systems of interest (eg, CV, pulmonary, GI, skin, ophthalmic, endocrine, or any systems with previously noted abnormal findings).
11. A complete ophthalmologic examination (including visual acuity, indirect funduscopy, slit lamp examination under dilatation, intraocular pressure measurement, corneal photography, and Schirmer's test) will be performed in all subjects at baseline (within 5 days prior to the first dose of CX-2009); within 5 days prior to Cycle 1, Day 1; Cycle 1 Day 15; Cycle 2, Day 1; and at the EOT Visit by an ophthalmologist. Subjects who report treatment-emergent changes in vision or other ocular symptoms will undergo repeat examinations prior to infusion every other cycle and as clinically indicated.
12. The ocular symptom assessment will include assessment of blurred vision and ocular discomfort. The ocular symptom assessment will be performed at Screening, prior to each infusion, and at the EOT Visit. If ocular toxicity occurs, see Section 5.5.3.2 and Section 5.5.4.1.
13. ECOG performance status should be assessed at Screening, Day 1 of every cycle, prior to each infusion, and at the EOT Visit.
14. Including CBC with differential, including platelet count and reticulocyte count, will be performed at Screening, preinfusion, weekly during treatment, and at the EOT Visit.
15. Serum chemistry will include ALP, AST/SGOT and ALT/SGPT, total bilirubin, calcium, phosphorus, BUN, creatinine, total protein, albumin, glucose, potassium, sodium, chloride, magnesium, uric acid, LDH, and hemoglobin A1c, if clinically indicated. Blood glucose should be fasting at Screening and as indicated to evaluate possible hyperglycemia. Calculated creatinine clearance is required at Screening. Laboratory assessments drawn on the day of infusion should be drawn preinfusion.
16. Serum chemistry will only include electrolytes (potassium, sodium chloride, and magnesium) on Days 8 and 22 of every cycle.

Table 14. Schedule of Procedures: Parts C1 and C2

Page 4 of 4

17. Coagulation will include PT/aPTT/INR at Screening, the EOT Visit, and as clinically indicated. If results are abnormal at Screening, then repeat prior to dosing or as clinically indicated.

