| q 21 days | every 21 days |
| RECIST | Response Evaluation Criteria in Solid Tumors |

| Abbreviation | Definition |
|---------------------|---|
| REP | response evaluable population |
| RP2D | recommended Phase 2 dose |
| SAE | serious adverse event |
| SAP | statistical analysis plan |
| SD | standard deviation |
| SD | stable disease |
| SOC | system organ class |
| SP | safety population |
| SRC | safety review committee |
| TEAE | treatment-emergent adverse event |
| TESAE | treatment-emergent serious adverse event |
| TMTB | total measured tumor burden |
| TTR | time to response |
| WHODrug | World Health Organization Drug Dictionary |

1. Purpose

This Statistical Analysis Plan (SAP) describes the statistical methodology and data handling for CytomX Therapeutics, Inc. protocol module number CTMX-M-2009-001 (A Phase 1-2, Open-Label, Dose-Finding, Proof of Concept, First-in-Human Study to Evaluate the Safety, Tolerability, Pharmacokinetics, and Pharmacodynamics of CX-2009 in Adults with Metastatic or Locally Advanced Unresectable Solid Tumors). The analysis specified in this SAP will be used to support safety review committee (SRC) and data and safety monitoring board (DSMB) analyses, publications, and FDA submissions. The proposed analyses may not be carried out if the sample size is not adequate.

The ICH guideline E3 "Structure and Content of Clinical Study Reports" was used as a guide to the writing of the plan.

This SAP is based on the following study documents:

- Protocol Core Amendment 01, 11 November 2016
- Protocol Module Amendment 06, 09 August 2017,
- Protocol Substudy V1.0, 04 May 2018
- Annotated Case Report Forms

The enrollment in CTMX-M-2009-001 was stopped by sponsor decision as of 07 July 2020, with a final enrollment of XX subjects into Parts A, A2, B, and C1.

2. Study Population

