The EOT Visit will be conducted 30 days (± 7 days) after the last infusion of CX-2009. Once a subject experiences progressive disease, they will continue to be monitored for survival. All subjects will return for Follow-Up Visits every 3 months after the EOT Visit for 1 year and then every 6 months to ensure resolution of toxicities and as applicable, confirm negative pregnancy status. During the EOT Visit, subjects will be followed for resolution of toxicity. Women of childbearing potential will undergo monthly pregnancy testing while on study drug and through 50 days after the last dose of CX-2009, or 6 months after the last dose of CX-072, as applicable, whichever is later. Thereafter, Follow-Up Visits will be conducted for survival information and may be performed by telephone.

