Shift tables will be created separately for Hematology and Blood Chemistry parameters, by dose level and by cancer type. The presentation in the table will be by CTCAE toxicity, and Grade 0 will be assigned for those values which are available and not assigned Grade 1, 2, 3 or 4. If the toxicity is bi-directional (e.g. Lymphocyte Count decreased, Lymphocyte count increased), then for the high direction Grade 0 will be assigned for the "low" direction. Similarly, for the low direction, Grade 0 will be assigned for the "high" direction. The shift tables will present shifts from baseline to worst post-baseline value. The worst post-baseline value could be any non-missing value collected after the first infusion up to and including 30 days after the last infusion.

Listings that include all laboratory results for any subject with any laboratory result outside of the normal range will be provided.

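### The laboratory shift tables stop at Day 30 after the last infusion, so an end-of-treatment sample drawn on time on Days 31 to 37 is left out

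*SAP*

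**What the plan says.** SAP 12.4 plans shift tables from baseline to worst post-baseline CTCAE grade for haematology and blood chemistry. The worst value may be "any non-missing value collected after the first infusion up to and including 30 days after the last infusion". The only other laboratory output in that section is listings: "Listings that include all laboratory results for any subject with any laboratory result outside of the normal range will be provided".

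The EOT visit window is in SAP 4.3: "The EOT Visit will be conducted 30 days (± 7 days) after the last infusion of CX-2009". The Module gives the same window (Appendix B, Table 13, footnote 24), and Core 9.9.2 also allows EOT procedures up to 7 days beyond Day 30. Haematology and serum chemistry are both scheduled at EOT in Tables 13 and 14.

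Three footnotes to Table 13 bear on timing:
- footnote 1: "Laboratory assessments may be performed up to 2 days prior to the visit";
- footnote 15: "Laboratory assessments drawn on the day of infusion should be drawn preinfusion";
- footnote 16: "Serum chemistry will only include electrolytes (potassium, sodium chloride, and magnesium) on Day 8 and Day 15 of every cycle".

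Table 14, for the 14-day regimen, has the equivalent chemistry rule: "Serum chemistry will only include electrolytes (potassium, sodium chloride, and magnesium) on Days 8 and 22 of every cycle".

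**The concern.** The schedule treats an EOT sample on Day 35 as on time. The analysis rule discards it from the shift tables, and nothing else in SAP 12.4 brings it back. Whether a mandated safety draw counts then depends on where in a permitted window the visit happened to fall.

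Any error goes in one direction: removing observations from a maximum can leave the worst grade unchanged or lower it, never raise it. The adverse event tables do not fill the gap, because SAP 12.1 also stops its summaries at Day 30 and only lists later events. An abnormality first seen at an on-time EOT visit on Days 31 to 37 can therefore be missing from every summary table.

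Under the supplied Module, full chemistry (AST, ALT, bilirubin, creatinine) is the most exposed. Mid-interval draws are electrolytes only and infusion-day draws precede the infusion. EOT is then the only full panel scheduled after the final infusion, unless the subject attends the next dosing visit and is not dosed. Liver tests matter for this drug: Module 1.3.4.1 reports Grade 3 AST and ALT increases as dose-limiting toxicities in Part C1.

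**Working it through.** The plan gives no figure of its own here, so the check is a count of days.

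**Inputs**
- EOT visit window: 30 ± 7 days after the last infusion (SAP 4.3).
- Shift-table cut-off: Day 30, inclusive (SAP 12.4).
- Draw allowance: 0, 1 or 2 days before the visit (Module, Table 13, footnote 1).

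**Permitted visit days.** 30 − 7 = 23 and 30 + 7 = 37, so Days 23 to 37, which is 37 − 23 + 1 = 15 days.

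**Does the sample count?** Draw day = visit day minus 0, 1 or 2. The sample counts if the draw day is 30 or earlier.

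| EOT visit day | Possible draw days | In the shift table? | Number of visit days |
|---|---|---|---|
| 23 to 30 | all by Day 30 | always | 8 |
| 31 | 29, 30 or 31 | only if drawn by Day 30 | 1 |
| 32 | 30, 31 or 32 | only if drawn by Day 30 | 1 |
| 33 to 37 | earliest is 33 − 2 = 31 | never | 5 |

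**Share of permitted visit days that lose the sample**
- Lost even with a draw 2 days early: 5/15 = 33%.
- Lost if every draw is on the visit day: (5 + 2)/15 = 7/15 = 47%.

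**Which Module version applies.** The SAP says it is based on "Protocol Module Amendment 06, 09 August 2017" (SAP 1). The supplied Module is later: it reports a 30 November 2019 data lock with 92 treated subjects (Module 1.3.4.1). SAP 4.2 gives 99 treated in all. The electrolytes-only schedule therefore cannot be confirmed for at least 92/99 = 93% of subjects. The draw allowance comes from the same supplied Module; without it, the result is the upper figure, 7 of 15. The conflict between the two windows does not depend on the Module version, because both limits are in the SAP.

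**After the fix.** With the window extended to the on-time EOT draw, all 15 permitted visit days count unless new anticancer therapy starts first. At present 8 always count and 2 count conditionally.

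**The case against.** The strongest reply is that Day 30 is a deliberate on-treatment boundary. The SAP uses it for adverse event summaries (12.1), for separating treatment from follow-up (11.1) and for on-treatment deaths (13.1.2). A visit tolerance and an analysis window need not coincide. Extending only the laboratory window would put a Day 34 Grade 3 AST in a shift table while an adverse event starting that day is only listed. It would also make the window differ between subjects.

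The consistency is real, and the cost of breaking it is real but small. For adverse events, though, Day 30 matches the Module's general 30-day reporting period (8.4 and 8.5), whereas required laboratory collection runs to the end of the EOT window. The SAP nowhere says that on-time EOT samples are meant to be excluded, and for vital signs (12.5.1) it selects values by protocol windows.

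Other limits on the concern stand:
- Late values are listed for any subject with an out-of-range result, though a listing does not correct a summary grade.
- Any draw by Day 30 counts, including unscheduled ones. Haematology is scheduled weekly during treatment, so it is less exposed than chemistry.
- The chemistry argument rests on a schedule that cannot be confirmed for most subjects.
- The tables are descriptive, SAP 12.1 plans no inferential safety tests, the recommended dose was chosen in November 2019 and enrolment has stopped.

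**Conclusion.** The concern holds, as a minor point. SAP 12.4 and SAP 4.3 together exclude a required, on-time EOT sample from the only laboratory summary planned in that section. The loss covers 5 to 7 of the 15 permitted visit days (33% to 47%). This follows from the two SAP limits and the 2-day draw allowance.

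It does not measure how many subjects or grades are affected; that needs the actual EOT draw dates, which the documents do not give. If few visits fell after Day 30, the tables will barely change. The direction is certain: any effect makes worst grades look better. The added weight on full chemistry is conditional on the supplied Module's schedule having applied to earlier subjects.

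**What to change.** In SAP 12.4, end the worst post-baseline window at the later of 30 days after the last infusion and the on-time EOT laboratory draw (by Day 37). Stop the extension earlier if new anticancer therapy starts. Leave the adverse event window in SAP 12.1 as it is.

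The cost is one SAP sentence and a small programming change. EOT samples and subsequent cancer treatment are already collected. Some worst grades may become slightly less favourable. Some subjects will contribute up to 37 − 30 = 7 more days of observation, and for them the laboratory window will be longer than the adverse event window.

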12.5 Other Safety Measures

12.5.1 Vital Signs

The mean change from baseline in vital signs will be presented in a figure for each vital sign parameter for both dose level and cancer type: Temperature (°C), Pulse rate (beats/min), Respiratory rate (breaths/min), Systolic Blood Pressure (mmHg), Diastolic Blood Pressure (mmHg), Pulse Oximetry (%) along with Weight (kg).

Separate lines will be presented by either dose level or cancer type as applicable in the figure.

The figures will be presented by nominal time since treatment start (weeks), and only values obtained in protocol-specified windows will be summarized. If more than one value is obtained in a protocol-specified window, the value closest to the target day in the window will be used. If there is more than one value equidistant from the target within the window, the value occurring before the target day will be used.

12.5.2 ECGs

All ECGs will be 12-lead. ECG assessments, including QTcF intervals, will be listed in chronological order by subject for any subject with an abnormal (not clinically significant or clinically significant) overall result.

13. Efficacy Analysis

13.1.1 Primary Efficacy Endpoint

The ORR is the primary efficacy endpoint. For solid tumors, response evaluation will be based on the RECIST criteria (v1.1) and ORR is defined as the proportion of subjects with complete response (CR) or partial response (PR) on two consecutive tumor assessments with scan dates at least 4 weeks apart according to RECIST (RECIST v1.1).

The primary efficacy analysis will be based on the REP. Exact 2-sided 95% Cis (using the Clopper-Pearson method) will be calculated for all proportion estimates.

A listing of tumor data including total tumor burden, RECIST v1.1 response assessments (target lesion evaluation, non-target lesion evaluation, and overall subject response) will be provided.

Response Assessment and Best Overall Response – RECIST v1.1

Efficacy outcomes will be summarized by dose level and by cancer type using RECIST v1.1 among the REP. The overall number of subjects for each dose; and the number, proportion, and 95% exact 2-sided CI (using the Clopper-Pearson method) of confirmed CR and PR, unconfirmed CR and PR, SD, PD, not evaluable (NE), overall response (CR + PR), disease control (CR + PR + SD) will be calculated. A summary table of the above response assessments by part using RECIST v1.1 among the REP will be provided. A swim lane plot of response assessment status over time using RECIST v1.1 will be produced.

The best overall response is the best response recorded from the start of study treatment until the end of treatment taking into account any requirement for confirmation. If the best overall response is determined before the end of treatment (e.g., for an interim data cut), then it is the best response recorded from the start of study treatment until the date of the data cut.

When no imaging/measurement is done at all at a particular time point, the subject is not evaluable (NE) at that time point. If only a subset of lesion measurements are made at an assessment, usually the case is also considered NE at that time point, unless a convincing argument can be made that the contribution of the individual missing lesion(s) would not change the assigned time point response (as may happen in the case of an assessment of PD).

Complete or partial responses may be claimed only if the criteria for each are met at a subsequent time point as specified in the protocol (i.e., ~8 weeks later and no

earlier than 4 weeks later). In this circumstance, the best overall response can be interpreted as in Table 1.

In the case of SD, measurements must have met the SD criteria at least once after study entry at a minimum interval of 7 weeks. If the first post-baseline response assessment is an SD and the assessment was less than 7 weeks from first dose of study drug, then the SD would be changed to NE. For the dose escalation parts of the study (i.e., parts A, A2), the reporting of CR/PR does not require confirmation as the primary objective is safety. Confirmation is required for the expansion cohorts (i.e., Part B).

Table 1: Best Overall Response Algorithm

| Overall Response First Time Point | Overall Response Subsequent Time Point | Best Overall Response |
|-----------------------------------|--|---|
| CR | CR | CR |
| CR | PR | SD, PD, or PR ^a |
| CR | SD | SD provided minimum criteria for SD duration met, otherwise, PD |
| CR | PD | SD provided minimum criteria for SD duration met, otherwise, PD |
| CR | NE | SD provided minimum criteria for SD duration met, otherwise, NE |
| PR | CR | PR |
| PR | PR | PR |
| PR | SD | SD |
| PR | PD | SD provided minimum criteria for SD duration met, otherwise, PD |
| PR | NE | SD provided minimum criteria for SD duration met, otherwise, NE |
| NE | NE | NE |

CR = complete response, PR = partial response, SD = stable disease, PD = progressive disease, and NE = not evaluable.

^a If a CR is truly met at first time point, then any disease seen at a subsequent time point, even disease meeting PR criteria relative to baseline makes the disease PD at that point (since disease must have reappeared after CR). Best response would depend on whether minimum duration for SD was met. However, sometimes 'CR' may be claimed when subsequent scans suggest small lesions were likely still present and in fact the subject had PR, not CR at the first time point. Under these circumstances, the original CR should be changed to PR and the best response is PR.

Tumor burden assessed using RECIST v1.1 will be calculated as the sum of (the longest diameter of target non-nodal lesions plus the short axis of target nodal lesions). The percent change from baseline will be plotted by time on study as a spider plot. The maximum percent change from baseline will be plotted in a waterfall plot. The spider and waterfall plots will include all visits regardless of whether or not a response assessment has been recorded (as long as all baseline target lesions were measured at the visit).

Additional efficacy figures may be provided by breast cancer subtypes (TNBC, HR+/HER2-, HER2+) as required.

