4.4 Withdrawal Criteria

Subject MUST discontinue the study drug for any of the following reasons:

- The subject experiences clinically significant or confirmed (RECIST) disease progression (or irRECIST in Parts D1, D2, E1, and E2), unless the subject experiences clinical benefit (as assessed by the Investigator); treatment beyond progression is permitted following consultation with the Medical Monitor or designee; however, the subject should be monitored and if continued progression occurs as defined by irRECIST, the subject must be withdrawn from the study drug;
- The subject is unwilling or unable to adhere to the Module;
- The subject withdraws consent or is lost to follow-up;
- The subject experiences an intercurrent illness that prevents further administration of study drug;
- The subject requires new/other anticancer treatment;
- The subject experiences an AE related to study drug which precludes further administration of the study drug;
- The subject experiences a prolonged treatment delay (as defined in [Section 5.5.4](#));
- The subject becomes pregnant, either prior to the first dose of study drug or at any time during treatment;

- In the Investigator's judgment, the subject should discontinue treatment;
- Death of the subject; or
- The Sponsor terminates the study.

Subjects who discontinue study drug administration for reasons other than TRAEs may be replaced to ensure the minimum number of subjects required for DLT evaluation is enrolled. Subjects who have enrolled in the study and have withdrawn prior to receiving the first dose will be designated as screen failures. The reason for subject withdrawal must be documented in the electronic case report form (eCRF).

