10.2.3.1. RECIST v1.1

Assessment of Measurable, Non-measurable, Target and Non-Target Lesions

During Screening, tumor lesions are to be categorized as measurable versus non-measurable and target versus non-target, as follows.

Measurable versus non-measurable

- Measurable lesions can be accurately measured in at least one dimension (longest diameter [LD] to be recorded) with a *minimum* size of: 10 mm by CT or MRI scan for non-nodal lesions and ≥ 15 mm in short axis for nodal lesions, 10 mm caliper measurement by clinical exam, or 20 mm by chest X-ray (CXR).
- Non-measurable: all other lesions, including small lesions (longest diameter < 10 mm or pathological lymph nodes with ≥ 10 to < 15 mm short axis) and truly non-measurable lesions (eg, pleural or pericardial effusion, lymphangitic involvement of skin or lung).

Target versus non-target

- Target: all measurable lesions up to a maximum of 2 lesions per organ and 5 lesions in total, representative of all involved organs, are to be identified as target lesions and measured and recorded at Screening. Target lesions are to be selected on the basis of their size (ie, those with the longest diameter) and suitability for accurate repeated measurement. The sum of the longest diameter for all target lesions is to be calculated and recorded in the eCRF as the baseline sum longest diameter. Target lesions cannot be biopsied at any time during the study.
- Non-target: all other lesions not classified as target lesions (or sites of disease) are to be identified as non-target lesions and are to be recorded in the eCRF. Measurement of non-target lesions is not required.

Disease response in target and non-target lesions will be assessed by the Investigator using RECIST v1.1 ([Eisenhauer et al, 2009](#)), according to the categories and criteria described in the table below. The best overall response for each subject will be reported as the best response documented over the sequence of objective statuses recorded using the categories and criteria in [Table 3](#).

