4.5 Discontinuation of Subjects from Treatment

Subject MUST discontinue the study drug for any of the following reasons:

- The subject experiences clinically significant or confirmed (RECIST v1.1) disease progression (or irRECIST in Parts D1 and D2);
- The subject is unwilling or unable to adhere to the Module;
- The subject withdraws consent or is lost to follow-up;
- The subject experiences an intercurrent illness that prevents further administration of study drug;
- The subject requires new/other anti-cancer treatment;
- The subject experiences a DLT or an adverse event related to study drug which precludes further administration of the study drug;
- The subject experiences a prolonged treatment delay (as defined in Section 5.5.4 of the CTMX-M-2009-001 Protocol Module);
- The subject becomes pregnant, either prior to the first dose of study drug or at any time during treatment;
- In the Investigator's judgment, the subject should discontinue treatment;
- Death of the subject; or
- The Sponsor terminates the study.

Subjects who discontinue study drug administration, for reasons other than TRAEs, may be replaced to ensure the minimum number of subjects required for DLT evaluation is enrolled. Subjects who have enrolled in the study and have withdrawn prior to receiving the first dose will be designated as screen failures. The reason for subject withdrawal must be documented in the electronic case report form (eCRF).

5. Study Endpoints

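### SAP 13.1.1 does not close the best-overall-response window at first RECIST v1.1 progression, so a response recorded after PD could count in ORR and CBR while PFS already has an event

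*SAP*

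**What the plan says.** **Window for best response.** SAP 13.1.1: "The best overall response is the best response recorded from the start of study treatment until the end of treatment", subject to any confirmation requirement; at an interim cut the window ends at the cut date. The Core (10.2.3.1) is no narrower: BOR is "reported as the best response documented over the sequence of objective statuses recorded".

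**ORR.** SAP 13.1.1 gives this definition: "the proportion of subjects with complete response (CR) or partial response (PR) on two consecutive tumor assessments with scan dates at least 4 weeks apart". It does not require those assessments to precede progression.

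**SAP Table 1.** Its rows begin with CR, PR or NE. None begins with PD, so the sequence PD, PR, PR is not resolved there.

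**Treatment after progression.** Module 4.4 makes progression a reason to stop, with an exception for clinical benefit: "treatment beyond progression is permitted following consultation with the Medical Monitor or designee". Monitoring goes on, and "if continued progression occurs as defined by irRECIST, the subject must be withdrawn from the study drug". SAP 4.5 gives the stopping reason as "The subject experiences clinically significant or confirmed (RECIST v1.1) disease progression" and does not carry the exception. The SAP names "Protocol Module Amendment 06, 09 August 2017" as its source, whereas the Module supplied reports data to November 2019.

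**Linked endpoints (SAP 13.1.2).** PFS has its event at first objective progression or death. DOR starts at the first response that is later confirmed and ends at the first documented progression or death. CBR16 and CBR24 count any subject whose BOR is CR or PR.

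**The concern.** ORR is the primary efficacy endpoint, and PFS and DOR are meant to describe the same course of disease. If BOR stays open after first PD, one subject can have a PFS event, then a first response, then a DOR whose end date precedes its start date. ORR would then include responses that PFS in the same plan places after failure, and CBR16 and CBR24 would inherit them.

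The route to this is open in both documents. The Module allows continued dosing after PD. The SAP's own stopping rule, as written, does not force a stop at a first PD that is neither clinically significant nor confirmed. Tumor assessments inside the treatment period but after first PD are therefore possible under either text. With few responders expected, each one matters to the estimate.

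**Working it through.** **1. One hypothetical subject taken through the definitions.** The scan interval is 8 weeks (Module, Tables 13 to 16). Suppose PD at week 8, treatment continued under Module 4.4, and PR at weeks 16 and 24.

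- ORR: two consecutive PRs, 24 - 16 = 8 weeks apart, which is at least 4. Counted as a responder.
- BOR: PR, because weeks 16 and 24 fall before end of treatment.
- CBR16 and CBR24: counted, through BOR = PR.
- PFS: event at week 8.
- TTR: 16 weeks, which is after the PFS event.
- DOR, literal: (first PD) - (first later-confirmed response) = 8 - 16 = -8 weeks (-56 days). If the first PR is at week 24 instead, 8 - 24 = -16 weeks.

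If BOR is cut at first PD, this subject is a non-responder with no DOR, and the endpoints agree.

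**2. The Module's planning figure.** Section 9 gives 8/40 = 20% with a 90% CI of 10% to 33%. The exact (Clopper-Pearson) limits are: lower = Beta quantile(a/2; x, n - x + 1), upper = Beta quantile(1 - a/2; x + 1, n - x).

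- 8/40, 90%: 10.36% to 33.20%. This reproduces the stated interval.
- 7/40, 90%: 8.51% to 30.37%.
- 6/40, 90%: 6.74% to 27.47%.

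The number of post-PD responders (0, 1 or 2 here) is an assumption; the documents give no count. In that illustration, losing one of 8 responders takes the lower limit below 10%.

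**3. The same counts with the SAP's interval.** SAP 13.1.1 specifies exact 95% limits.

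- 8/40, 95%: 9.05% to 35.65%.
- 7/40, 95%: 7.34% to 32.78%.

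Neither excludes 10%, so no crossing occurs between 7 and 8 responders.

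**4. Actual size (SAP 4.2).** Treated: 37 + 39 + 10 + 3 + 10 = 99, of whom 3 were in Part B.

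- Part B: one post-PD responder would move 0/3 (95% CI 0% to 70.8%) to 1/3 (0.8% to 90.6%). Both are uninformative.
- All subjects in the Module's November 2019 summary (1.3.4.2): 2/92 = 2.2% confirmed PR; one more gives 3/92 = 3.3%. Those 92 span many doses and both schedules and are not the Part B cohort.
- Parts A and A2, including the mTPI-2 cohort: 37 + 10 + 39 = 86 subjects. SAP 13.1.1 does not require confirmation for reporting CR/PR in these parts, so a single post-PD PR could be reported as a response. It would have no DOR, because DOR is limited to confirmed responders.

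**The case against.** The strongest reply is that this is a gap in wording with almost nothing behind it.

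- **Few post-PD scans.** Response scans are scheduled until progression (Module Tables 13 to 16; Core 10.2.3), and SAP 4.3 and 13.1.3 move progressed subjects to survival follow-up. This stands as a limit on frequency. It does not close the route, because Module 4.4 requires continued monitoring of subjects treated beyond progression.
- **A PR after PD is hard to reach.** Core Table 4 keeps a time point at PD while a new lesion is present. The first PD must therefore come from growth of existing disease, or from a new lesion that resolves, followed by a fall to at least 30% below baseline. This stands.
- **Negative DOR is a strained reading.** A duration from response to progression naturally means progression after that response. That is a fair reading, and the negative value arises only if first documented progression is taken literally, and only for confirmed responders. One added word would settle it.
- **It would be seen.** The SAP's response listing and swim-lane plot would show a PD-then-PR sequence. True, but neither display removes the subject from ORR.
- **RECIST v1.1 is cited.** The SAP nevertheless writes its own window, and that window runs to end of treatment.

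A reader might also infer that under the SAP's stopping rule end of treatment coincides with first PD, so that only the later Module text creates the problem. SAP 4.5 does not support that: its condition of clinically significant or confirmed progression leaves room for dosing after a first PD.

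**Conclusion.** The gap is real: followed literally, the BOR and ORR rules could admit a response recorded after first PD, at odds with PFS in the same plan. CBR16 and CBR24 share the gap. The conclusion rests on the SAP and Core definitions as written and on continued dosing after PD being possible.

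Few or no subjects are likely to be affected. Part B has 3 subjects, post-PD scans should be uncommon, and a later PR has to meet the conditions above.

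Two stronger readings should be resisted. First, a reader might infer that a single such subject decides whether an ORR of 10% is excluded. That holds only in the Module's 90% planning illustration with 40 subjects; it does not hold for the SAP's 95% interval, and no 40-subject cohort was enrolled. Second, a reader might infer that the reported ORR is inflated. The documents report no post-PD response, so this is a rule to tighten and not a demonstrated bias. The change is still worth making, because it costs little and makes ORR, DOR and PFS consistent.

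**What to change.** In SAP 13.1.1, define BOR and ORR from assessments up to and including the earliest of first documented RECIST v1.1 PD, start of new anti-cancer therapy, or end of treatment (or data cut). The therapy cut-off is largely covered already, since needing new anti-cancer treatment is a reason to stop study drug, but stating it matches the PFS censoring rule. CBR16 and CBR24 then follow without further change.

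List any CR or PR recorded after first PD separately, outside ORR. In SAP 13.1.2, state that DOR ends at the first PD after the response, or at death. Adding a PD-first row to Table 1 would make the rule explicit.

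Reconcile SAP 4.5 with Module 4.4 on treatment beyond progression, and update the Module version on which the SAP relies. Which clinical rule applies is for the sponsor to settle.

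Cost: a few sentences in the SAP and a small programming change. No new data are needed.
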